7.6 Off-study criteria

Patients who enroll on Step 1 will be followed for survival status prior to step 2 if they: 1) progress on chemotherapy, 2) experience toxicity that is deemed to be unacceptable by the treating physician prior to the minimum requirements for induction chemotherapy (i.e. 4 cycles of platinum doublet therapy, 3 months of erlotinib/ afatinib, or 3 months of crizotinib), or 3) refuse randomization. If this occurs, they will remain on study only until proceeding to LCT at the end of induction chemotherapy, if applicable (e.g. without any maintenance therapy or second line systemic therapy), and will be followed for survival status at the conclusion of LCT. Allowing patients to remain on study until the time of LCT will allow for tissue collection if the patient proceeds to surgical resection. Patients who do not proceed with randomization but do not proceed immediately to LCT (receiving maintenance therapy or further systemic therapy) will be followed for survival status immediately after proceeding to maintenance therapy or further systemic therapy.

Patients who continue to step 2, or enroll at step 2, will be followed for survival status at the time of RECIST progression. Patients that are randomized to the immediate LCT arm will be followed for survival status immediately after experiencing RECIST progression. Patients that are randomized to the delayed LCT arm that experience progression will remain on study until the completion of LCT *only if LCT is planned within 6 weeks*. In this scenario, the patient will be followed for survival status at the conclusion of LCT. If no LCT is planned within this timeframe (i.e. if second line chemotherapy is planned and not LCT), the patient will be followed for survival status immediately after experiencing RECIST progression. Allowing patients to remain on study until the time of LCT will allow for tissue collection at that time if the patient proceeds to surgical resection. At that time, crossover can occur between treatment arms, at the treating physician's discretion. Crossover can also occur due to treatment toxicity or an increase in the size of disease that does not meet the criteria of RECIST progression. Patients who do not meet the criteria for RECIST progression and crossover to the alternate arm (e.g., crossover for a reason other than progression) will remain on study and will be followed for survival status.

8. Evaluation of Outcomes of Interest

The primary outcome of this study is PFS. To evaluate this endpoint, radiographic evaluations of the primary and metastatic sites should be conducted at an interval of approximately every 8 weeks after randomization (Step 2) regardless of whether the patient is receiving LCT, maintenance therapy or surveillance, as is standard at our institution (Appendix A). Evaluation will include 1) A PET/CT scan or CT scan of the chest in all patients, and 2) An MRI of the brain or a CT scan of the brain in patients with known brain metastases.

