1.2 Secondary Objectives

The secondary objectives of this study will be to:

- Determine the overall survival
- Safety/tolerability of LCT
- Time to progression of prior metastatic lesions
- Time to appearance of new metastases (CNS vs. extra-CNS, treated lesion vs. new site)
- Quality of life

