4.0 Treatment Plan

Prior to randomization, eligible patients will have received 4-6 cycles of induction chemotherapy, erlotinib or afatinib (for patients with known EGFR mutations) or crizotinib (for patients with known EML4-ALK fusion) without evidence of RECIST progression. They will be registered and then randomized in a 1:1 fashion to either immediate or no/delayed LCT. All patients will be followed until progression of disease is documented or two years after randomization, whichever comes first. Patients with metastases involving the brain or spinal cord, or metastatic lesions causing symptoms requiring palliation (e.g., bone, soft tissue) may be treated with surgery or radiotherapy prior to the completion of induction chemotherapy (randomization).

The following imaging studies are suggested after first-line therapy to assess the number of sites: 1) imaging of the brain with either a magnetic resonance imaging (MRI) scan (preferred) or a CT scan of the brain with contrast, and 2) systemic imaging with a positron emission tomography/computed tomography (PET/CT) scan or a CT scan of the chest/abdomen/pelvis with contrast. Other studies, such as a bone scan, and aspiration of pleural fluid, are at the treating physician's discretion.

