4.2.3.6 Dose Calculation

Doses are to be calculated with CT based heterogeneity corrections, i.e. corrections are made for density differences between air spaces, lungs, water-density, or bone tissue.

5. Symptom Assessment during Protocol Treatment

A) As noted below in “Evaluation of Outcomes of Interest,” patients will be evaluated in the clinic for toxicity at follow-up visits every 8 +/- 2 weeks until 1 year, and then less frequently thereafter. Concordant with these clinic visits, the research team will capture toxicities in our toxicity log that meet the following criteria, per institutional policy: a) severe, defined as CTCAE v4.0 Grade 3 or higher, 2) unexpected, or 3) unanticipated. In addition, we will ensure that all relevant toxicities (severe, unexpected, or unanticipated) are documented appropriately in the medical record.

B) *Multiple-symptom assessment tool (optional)*. Symptoms will be measured by the Lung Cancer module of the MDASI²⁴. The MDASI is a multiple-symptom measure of cancer-related symptoms²⁵ that is sensitive to disease and treatment changes in lung cancer. This instrument is brief, easily understood, and validated in the lung cancer population. Patients rate the intensity of physical, affective, and cognitive symptoms on 0–10 numeric scales, ranging from “not present” to “as bad as you can imagine.” Patients also rate the amount of interference with daily activities caused by symptoms on 0–10 numeric scales, ranging from “did not interfere” to “interfered completely.” The MDASI-LC has 3 additional items known to be important in assessing patients with MM or MM therapies (constipation, coughing, sore throat). The MDASI-LC takes less than 5 minutes to complete. It can be completed at home using the web or an interactive voice response-computer system that calls the patient to have them rate their symptoms and symptom interference²⁶. Symptom severity and interference over time will be a secondary endpoint. The MDASI is included in Appendix C, and this data will be collected from each patient at each follow-up visit as described in the *Evaluation of Outcomes of Interest* section (every 6-8 weeks for the first year).

6. Optional Procedures after Induction Chemotherapy

A) Tissue specimen collection for biomarker analysis:

[figure not shown]

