7.5 Statistical Analysis Plan

Descriptive statistics will be provided to summarize the patient characteristics and toxicities by the treatment arms (immediate LCT and delayed/no LCT groups). Chi-square test or Fisher's exact test will be applied to compare patient characteristics between the two arms. The balance of the five prognostic covariates (used in the Pocock-Simon's dynamic allocation method) between the two arms will be examined as well. For the primary endpoint, PFS, Kaplan-Meier estimate will be computed, and the log-rank test will be performed to compare the difference of PFS between the two arms. Cox regression model will be applied to correlate PFS with potential covariates in both the univariate and multi-covariate analyses. Patients are considered evaluable for efficacy if they receive at least one of the intended local consolidation therapy. Both the intent-to-treat analysis and analysis among the evaluable patients will be performed. The corresponding results will be compared and contrasted. For the secondary endpoints, similar analysis will be performed on the overall survival and other time-to-event endpoints. Safety and tolerability of the immediate LCT arm and delayed/no LCT arm will be summarized by descriptive statistics. Quality of life will be analyzed by the repeated measures analysis of variance to count for the change before and after treatment and during the follow-up period. Proper transformation will be performed if necessary to transform data to be closer to the Gaussian distribution. All the statistical analyses will be two-sided with a P-value of 0.10 or less considering statistically significant.

Note that the MDACC DSMB will be providing study-wide oversight in regards to the endpoints described above.

To account for patients that crossover for reasons other than RECIST progression of disease (e.g. toxicity, growth of the malignancy that does not constitute RECIST progression), censoring will occur at the time of crossover for our primary analysis. In addition, a secondary time varying covariate Cox model analysis will be done to assess the impact of crossover without RECIST progression.

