Appendix A. Timeline of evaluations before, during and after randomization.

Study Test	Baseline (prior to randomizati on)	After randomizat ion, prior to treatment – Treatment= 0 weeks	8 weeks +/- 2 weeks	16 weeks +/- 2 weeks	24 weeks +/- 2 weeks	32 weeks +/- 2 weeks	40 weeks +/- 2 weeks	48 weeks +/- 2 weeks
PET/CT or CT Scan Chest	X (PET/CT scan preferred)		X	X	X	X	X	X
MRI Brain or CT Head	X (all patients, MRI Brain preferred)		X (if brain mets)	X (if brain mets)	X (if brain mets)	X (if brain mets)	X (if brain mets)	X (if brain mets)
Blood-Based Biomarkers (optional study)		X	X	X	X	X	X	X
Toxicity Assessment		X	X	X	X	X	X	X
Quality of Life Symptom Assessment (optional study)		X	X	X	X	X	X	X

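### No toxicity window is set after LCT, and the off-study rules end toxicity observation at different points in the two arms

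*Combined protocol and SAP*

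**What the plan says.** Section 1.2 lists "Safety/tolerability of LCT" as a secondary objective. Section 7.5 gives the analysis: "Safety and tolerability of the immediate LCT arm and delayed/no LCT arm will be summarized by descriptive statistics". It mentions no allowance for unequal observation time.

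Four places bear on how long toxicity is observed:

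- **Section 5** says patients are "evaluated in the clinic for toxicity at follow-up visits every 8 +/- 2 weeks until 1 year, and then less frequently thereafter". Toxicities that are grade 3 or higher, unexpected or unanticipated go into a log. No stopping point at progression is given.
- **Appendix A** has a "Toxicity Assessment" row at week 0 and at weeks 8, 16, 24, 32, 40 and 48. Week 0 is the time after randomization and before treatment. The row is not tied to LCT and not conditioned on progression.
- **Section 4.0** says: "All patients will be followed until progression of disease is documented or two years after randomization, whichever comes first".
- **Section 7.6**, the off-study criteria, says: "Patients that are randomized to the immediate LCT arm will be followed for survival status immediately after experiencing RECIST progression". Delayed-arm patients who progress stay on study through LCT only if it is planned within six weeks. For them: "In this scenario, the patient will be followed for survival status at the conclusion of LCT". If no LCT is planned in that time, survival follow-up starts at progression.

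The reason section 7.6 gives for keeping patients on study until LCT is tissue collection, not safety. It also says that patients who cross over without RECIST progression stay on study, and it describes them too as being followed for survival status.

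**The concern.** Section 4.2.1 describes LCT in the delayed arm as given at progression or toxicity. The event that commonly triggers LCT there is therefore the same event that closes on-study follow-up. In the immediate arm LCT comes first, and observation continues for as long as the patient stays progression-free, up to two years.

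If survival follow-up carries no toxicity collection, the by-arm safety summary rests on windows of different length that start from different points. LCT toxicity is under-ascertained in the delayed arm. In the immediate arm it is lost after progression, so later toxicity is seen only in patients whose disease remains controlled. At stake is a named secondary objective; the primary PFS analysis is not affected.

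**Working it through.** **1. Observation after LCT, by route (sections 4.0 and 7.6 read together)**

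| Route | On-study follow-up ends | Observation after LCT |
|---|---|---|
| Immediate arm | RECIST progression or two years | From end of LCT to that point |
| Delayed arm, LCT at progression, planned within six weeks | Conclusion of LCT | None |
| Delayed arm, LCT not planned within six weeks of progression | Progression | None; a later LCT itself is also outside on-study follow-up |
| Crossover without RECIST progression | Patient stays on study | Possibly captured; wording unclear |

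Section 5 and Appendix A do not carry these end points, so a site could follow either set of rules.

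**2. Check of the design inputs (section 7.4)**

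Inputs: medians 4 and 7 months; 94 patients randomized 1:1 (47 per arm; section 4.0 for the ratio); accrual A = 37.6 months; further follow-up F = 9 months. With exponential PFS, λ = ln 2 / median and

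p = 1 − [exp(−λF) − exp(−λ(A+F))] / (λA).

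- Delayed: p = 0.968, and 47 × 0.968 = 45.5 events.
- Immediate: p = 0.892, and 47 × 0.892 = 41.9 events.
- Total 87.4, against the stated 87.

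The exponential model with these medians reproduces the plan's figure, so it is used below.

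**3. PFS events by time t: 1 − 0.5^(t/median)**

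- 6 months: delayed 1 − 0.5^(6/4) = 65%; immediate 1 − 0.5^(6/7) = 45%.
- 12 months: delayed 1 − 0.5^(12/4) = 88%; immediate 1 − 0.5^(12/7) = 70%.

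Section 7.1 counts death as a PFS event. A patient who has died is not losing toxicity follow-up to the off-study rule, so these are upper bounds on loss from that rule. They run from randomization, not from LCT.

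**4. Observation time from randomization to a PFS event**

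- Mean time capped at 24 months, (1 − exp(−24λ))/λ: 5.7 months delayed, 9.2 months immediate, ratio 1.6.
- Expected number of the six Appendix A visits (weeks 8 to 48) reached before a PFS event, summing 0.5^(t/median) over the visits: 2.3 delayed, 3.3 immediate.

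Delayed-arm patients who stay on study through LCT gain the time to the end of LCT, but nothing after it.

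**5. Immediate arm, time after LCT**

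The documents do not give the duration of LCT. Assuming d = 1 to 3 months, the share observed for at least 6 months after LCT is 0.5^((d+6)/7): 50% at d = 1 and 41% at d = 3.

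**6. Delayed arm, patients with no window after LCT**

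By 24 months, 1 − 0.5^(24/4) = 98.4% have a PFS event. The share of progressors who receive LCT within six weeks is not stated. Assuming 10% to 75%:

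- 47 × 0.984 × 0.10 = 4.6, about 5 patients.
- 47 × 0.984 × 0.75 = 34.7, about 35 patients.

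This treats all PFS events as progressions, so it errs on the high side for any given share.

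**The case against.** The strongest reply is that no sentence says toxicity collection stops. Section 5 and Appendix A set schedules that progression does not interrupt. Section 7.6 also uses the survival-status wording for crossover patients whom it keeps on study, so that wording alone need not exclude toxicity capture. This stands: the end of collection is inferred from section 4.0 and the off-study rules. It does not remove the problem. Section 4.0 ends follow-up at progression, section 7.6 stands under an off-study heading, and nothing sets a window after LCT.

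Further limits also stand:

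- A reader might infer that all delayed-arm LCT goes unobserved. It does not follow: patients who cross over for toxicity, or for growth short of RECIST progression, stay on study.
- A reader might take the 65% and 88% to mean that nearly all delayed-arm LCT is affected. Those are PFS-event proportions, deaths included, and not shares of LCT.
- A reader might infer that delayed LCT will be reported as safer than immediate LCT. Section 7.5 plans descriptive summaries by randomized arm and no such contrast.
- Visits continue, less often, after the first year, so progression-free immediate-arm patients can be observed for up to two years, not one.
- The documents give no onset times for LCT toxicity, so the number of missed events cannot be calculated.

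The adverse event rules in section 8.1 do not fill the gap. They govern prompt reporting of external events to the IRB and do not supply data for the by-arm summary.

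**Conclusion.** The concern holds in this form. Sections 4.0 and 7.6, followed as written, leave LCT given at RECIST progression in the delayed arm without any toxicity observation afterwards. LCT not planned within six weeks of progression falls outside on-study follow-up. In the immediate arm, toxicity after progression is lost. Section 5 and Appendix A point the other way, or are silent, and the sections must be reconciled. The by-arm summary of LCT safety therefore rests on unequal windows.

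The size depends on exponential PFS at the design medians and on two quantities the documents do not give: the duration of LCT and the share of delayed-arm progressors who receive it. For the second, 10% to 75% gives roughly 5 to 35 of 47 patients. The documents do not support a stronger claim that toxicity collection is expressly stopped, or that the safety comparison is biased by a known amount.

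**What to change.** In section 7.6, state that grade 3 or higher and unexpected toxicity is collected for one fixed window after the last LCT, the same in both arms and regardless of RECIST progression. The sponsor should set its length. Collect it by chart review during survival follow-up; the plan gives no schedule or method for that follow-up, so add one. Record there the date and site of any LCT given later. Bring section 4.0, section 5 and Appendix A into line, and say explicitly whether toxicity is collected for patients who cross over without RECIST progression.

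In section 7.5, report LCT toxicity per LCT-treated patient in each arm, timed from LCT, with the observation time by arm beside it.

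The cost is protocol wording and a little more data collection. Later toxicities may overlap with second-line therapy, so attribution must be recorded. Randomization, sample size and the primary analysis do not change.

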8.1 Reporting Requirements for External AEs

External AEs (EAEs) Requiring Prompt Reporting to IRB

The MD Anderson IRB requires that the investigators submit a prompt report only for external AEs that meet the following criteria for an unanticipated event:

- serious,
- unanticipated,
- related (definitely, probably, or possibly related)

Most of the time, these are events that would require changes in the Investigator Brochure (IB), the informed consent document, or the protocol.

The Sponsor in this situation is responsible for determining if the external AE meets the criteria for prompt reporting to the IRB and the FDA.

Investigators should refer to the 2009 FDA and January 2007 OHRP guidance for reporting of UAEs and UDAEs. Isolated reports should be first reported to the Sponsor in most instances and may not require reporting to the IRB unless the Sponsor ascertains the event to be reportable.

A meaningful analysis or explanation of the reported external event is necessary to enable IRB to make complete determinations in regard to the protection of participants.

Reporting Timeline for prompt reporting:

1. **Within 5 working days from the time the research team becomes aware of the event =**
Unanticipated deaths that are attributed by the Sponsor as definitely, probably or possibly

related to study intervention that have occurred within 30 days after the last day of active study intervention.

2. **Within 5 working days from the time the research team becomes aware of the event** = All other serious, unanticipated and definitely, probably or possibly related AEs.

Unanticipated EAEs are required to be reported to the IRB beginning from the date on the MD Anderson IRB letter that approved the protocol.

The MD Anderson IRB does not require the investigators to report EAE that do not meet the criteria for unanticipated events.

The principal investigator (PI) is not required to accept or submit reports to the IRB, that are not compliant with the FDA's final rule or OHRP's reporting policies

9. References

2. Reck M, von Pawel J, Nimmermann C, Groth G, Gatzemeier U. [Phase II-trial of tirapazamine in combination with cisplatin and gemcitabine in patients with advanced non-small-cell-lung-cancer (NSCLC)]. *Pneumologie* 2004;58:845-9.

Appendix A. Timeline of evaluations before, during and after randomization.

Study Test	Baseline (prior to randomizati on)	After randomizat ion, prior to treatment – Treatment= 0 weeks	8 weeks +/- 2 weeks	16 weeks +/- 2 weeks	24 weeks +/- 2 weeks	32 weeks +/- 2 weeks	40 weeks +/- 2 weeks	48 weeks +/- 2 weeks
PET/CT or CT Scan Chest	X (PET/CT scan preferred)		X	X	X	X	X	X
MRI Brain or CT Head	X (all patients, MRI Brain preferred)		X (if brain mets)	X (if brain mets)	X (if brain mets)	X (if brain mets)	X (if brain mets)	X (if brain mets)
Blood-Based Biomarkers (optional study)		X	X	X	X	X	X	X
Toxicity Assessment		X	X	X	X	X	X	X
Quality of Life Symptom Assessment (optional study)		X	X	X	X	X	X	X

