1.3 Study Design

This is a Phase II open-label study in NSCLC patients with oligometastatic disease (defined here as 1-3 observable metastases after the completion of chemotherapy) who have no evidence of disease progression after standard first-line therapy (4-6 cycles of platinum-doublet chemotherapy, with or without bevacizumab; erlotinib or crizotinib alone or in combination with other regimens are also acceptable options for patients with tumors known to bear a known EGFR activating mutation (for erlotinib or afatinib) or EML4ALK fusion (for crizotinib). Patients will be enrolled either prior to completing 4 cycles of induction

chemotherapy (step 1 enrollment) or after the completion of at least 4 cycles of chemotherapy (step 2 enrollment). In either case, they will be randomized during Step 2 to the “immediate LCT” arm consisting of LCT followed by either surveillance or maintenance therapy at the discretion of the treating physician, compared to delayed/no LCT. When undergoing LCT (in either arm), patients will receive consolidative therapy with either radiotherapy or surgery for all residual lesions (primary and metastases). The choice of the specific consolidative therapy will be made by the treating physician(s). Consultation with a multidisciplinary team including a radiation oncologist and thoracic surgeon is encouraged.

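### The first optional MDASI-LC falls after open-label randomization, so the quality-of-life baseline and the comparison of change built on it are open to bias

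*Combined protocol and SAP*

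**What the plan says.** Section 1.3 describes the design: "This is a Phase II open-label study in NSCLC patients with oligometastatic disease".

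Appendix A opens with two separate columns before the 8-week visit. One is the pre-randomization baseline; the other is headed "After randomizat ion, prior to treatment" (the split word comes from the text extraction) and is set at week 0. In the row "Quality of Life Symptom Assessment (optional study" the pre-randomization cell is empty. The first mark is at week 0, followed by weeks 8, 16, 24, 32, 40 and 48.

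Section 5B makes the questionnaire optional, states that "Symptom severity and interference over time will be a secondary endpoint", and says that "this data will be collected from each patient at each follow-up visit". Section 6C refers back to Section 5B. Quality of life is also a listed secondary objective in Section 1.2.

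Section 7.5 plans a repeated-measures analysis of variance "to count for the change before and after treatment and during the follow-up period". It does not define a baseline, and it sets a two-sided significance level of 0.10 for all analyses.

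**The concern.** A baseline measured before randomization cannot depend on the arm. One measured after open-label randomization can. The MDASI-LC asks patients to rate the last 24 hours, and some of its items (distress, sadness, disturbed sleep, mood, enjoyment of life) could plausibly respond to news of the assignment. Since the week-0 form is the only score available from before treatment, any such response enters the starting point from which Section 7.5 measures change. A difference between arms in change could then partly reflect different starting ratings and not what happened after treatment. The reverse is also possible: a real difference could be masked.

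**Working it through.** The documents give no MDASI-LC effect size, standard deviation or power figure, so there is no stated figure to reproduce. The check has three parts.

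**1. Is the schedule read correctly?** The Appendix A header has 9 cells (a label and 8 time columns), and so does the quality-of-life row. They align: blank before randomization, then 7 marks from week 0 to week 48. The two imaging rows are marked in the pre-randomization column. The blank is therefore not an extraction fault.

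**2. Does another section supply an earlier form?** No. Section 5B speaks of follow-up visits, Section 6C adds nothing, and the baseline at randomization in Section 6B concerns blood samples.

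**3. What would a shift at week 0 do?** Define, for immediate minus delayed/no LCT:
- tau: the difference at a follow-up visit apart from any effect of knowing the arm
- d: the difference in mean week-0 score caused by knowing the arm
- k: the fraction of d still present at follow-up (0 = gone, 1 = fully persistent)
- rho: the within-arm correlation of week-0 and follow-up scores, with equal SDs

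The expected contrasts are:
- change from week 0: (tau + k·d) − d = tau − (1 − k)·d
- adjusted for week 0: (tau + k·d) − rho·d = tau − (rho − k)·d
- either method with a pre-randomization score: tau + k·d

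With k = 0 the errors are −d, −rho·d and 0. With k = 1 they are 0, +(1 − rho)·d and +d.

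**Illustration for a transient shift (k = 0, tau = 0).** From the documents: 94 randomized 1:1, so at most 94/2 = 47 per arm, and two-sided 0.10 (critical value 1.645). Assumed, because the documents give nothing: SD = 2 points, rho = 0.5, and d = 0.25 to 1.0 points.
- SE(change) = SD·√(2(1 − rho))·√(2/47) = 2 × 1 × 0.2063 = 0.413
- SE(adjusted) = SD·√(1 − rho²)·√(2/47) = 2 × 0.866 × 0.2063 = 0.357
- False-positive rate = 1 − Φ(1.645 − |bias|/SE) + Φ(−1.645 − |bias|/SE)

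| d (assumed) | Bias, change score | False-positive rate | Bias, adjusted | False-positive rate |
|---|---|---|---|---|
| 0.25 | −0.25 | 16% | −0.125 | 12% |
| 0.5 | −0.5 | 34% | −0.25 | 18% |
| 1.0 | −1.0 | 78% | −0.5 | 40% |

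For d = 0.5, the ratios |bias|/SE are 0.5/0.413 = 1.21 and 0.25/0.357 = 0.70. Over SD 1.5 to 2.5 and rho 0.3 to 0.7, the same d gives 21% to 67% for the change score and 12% to 48% for the adjusted contrast. Fewer than 47 respondents per arm would lower these rates but leave the bias in points unchanged.

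**The case against.** The best reply is that nothing here demonstrates bias. No section says when a patient learns the arm relative to the week-0 form. Section 6B gives randomization as an example of the blood baseline, and Appendix A marks that sample in the same column, so the two may share a visit. Section 7.5 specifies neither a change score nor a between-arm contrast. The transient-shift assumption is also favourable to the concern: every later form is unblinded, and if the effect of knowing the arm persists, subtracting week 0 removes some or all of it, whereas a pre-randomization baseline leaves it in. All of this stands. It limits the claim to possible bias of unknown size and direction, but it does not supply a baseline that is independent of the arm.

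Four stronger readings are tempting, and the documents do not support them:
- **That the quality-of-life result could not be read as an effect of LCT.** The week-0 form precedes treatment, so LCT itself has not altered it. The five items named above are 5 of 22; most of the others are physical symptoms. Unblinded reporting at follow-up belongs to the open-label design.
- **That patients can opt out after learning their arm.** Signed consent is required before randomization (3.1.1.12). The consent pages are not in the reviewed file, so whether the optional choice is recorded there cannot be checked.
- **That surveillance patients have no date for the week-0 form.** The column is tied to randomization, as is imaging in Section 8.
- **That the toxicity row has the same fault.** Under Section 5A, toxicity is evaluated in the clinic and logged when it is CTCAE grade 3 or higher, unexpected or unanticipated. It is not a patient self-rating.

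**Conclusion.** The point holds as a vulnerability, not as demonstrated bias. The only pre-treatment MDASI-LC score is scheduled after open-label randomization and may be given with knowledge of the arm. A shift of d confined to week 0 would bias a change score by d and a baseline-adjusted contrast by about rho·d; a persistent shift would partly cancel in change from week 0, and wholly if nothing of it had faded. The false-positive rates above rest on assumed values of d, SD and rho and on a shift that has gone by follow-up. They illustrate sensitivity and do not estimate what will happen in this trial.

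The scope is one optional secondary endpoint. PFS, the 87 events and the 94 randomized patients are unaffected. A pre-randomization form removes the allocation effect from the baseline only; awareness at later visits remains. What it secures is a contrast with a clear meaning (the effect of assignment, awareness included) in place of one that depends on an unknown k. It is a cheap improvement and worth making.

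**What to change.** - **Appendix A:** put the first quality-of-life mark in the pre-randomization baseline column, after induction and before the arm is assigned.
- **Section 5B:** state that this form is completed before randomization.
- **Section 7.5:** name that score as the baseline and enter it as a covariate in the repeated-measures model. If the week-0 form is kept, treat it as a post-randomization measurement.
- **Patients already randomized:** report week-0 scores and completion by arm, and add a sensitivity analysis comparing post-treatment scores without subtracting week 0.

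The cost is one short form before randomization. Section 5B puts it at under 5 minutes, with completion at home by web or telephone possible. Some forms will come from patients who then decline randomization (Section 7.4 expects 19 refusals). Sample size and event count do not change.
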